Cover Page

Official Title: Evaluating the Effectiveness of Migraine CarePath

NCT Number: NCT05067725

Date of document creation: 10/10/2022

Statistical Analysis Plan

The CMSL sites will be clustered-randomized based on clinic location, patient volume and patient to provider ratio to the intervention and control arm. Baseline characteristics (e.g. sex, age, race, ethnicity, insurance plans etc.) will be collected and compared between groups to ensure consistency for the investigation of all aims and sub-aims. Where applicable, statistical tests will be 2-tailed. T-tests will be used to measure the statistical significance of continuous data between groups. Chi-Square tests will be used to measure the statistical significance of categorical data.

All primary and secondary outcomes will be assessed using a GLM model and appropriate link and distribution, e.g. multivariate Poisson/Linear regression with robust standard errors. We will check model assumptions and power to produce constructive analysis and determine the effects of the interventions on the final outcomes. All analyses will be two-tailed and results will be reported both as effect estimates (with standard errors and p values) as well as effect estimates with 95% confidence intervals. We will estimate average treatment effects (ATEs) to mitigate biases in intervention-control group comparisons. These biases arise from permanent differences between the groups as well as biases in pre-post comparisons resulting from secular trends unrelated to the intervention. In the simplest case, program effects are assessed by comparing pre-post differences in outcomes between practices exposed (Y12–Y11) and not exposed (Y22– Y21) to the BPA, i.e. (Y12-Y11)-(Y22-Y21). We will calculate program effects on practicelevel outcomes using a semi-parametric, causal analysis if required. We will compare differences in outcomes between intervention and control practices. Multiple periods will be examined, when possible, to assess potential "burn-in" (effects of the intervention). Demographic variables that are significantly different between groups (p < 0.05) will be included in a multivariable (adjusted) model.

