The analysis will be conducted based on the principle of "intention-to-treat (ITT)." All patients who consented and met the inclusion criteria will be included in the analysis per the group they were recruited into. For missing data via survey collection inclusion of only patients who completed all 3 sets of questionnaires could bias results toward improvement. To minimize this potential bias, a last observation carried forward (LOCF) technique will be applied. Results from the LOCF technique will be further compared to those from the measured data to assess the impact of loss to follow u

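### The intention-to-treat set is defined by consent under site randomisation, and neither the p < 0.05 demographic rule nor the pre-post contrast fully guards against the arms recruiting different patients

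*SAP*

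**What the plan says.** The SAP is a short unnumbered document. Four of its statements bear on this point.

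- **Allocation (first paragraph).** "The CMSL sites will be clustered-randomized based on clinic location, patient volume and patient to provider ratio to the intervention and control arm". The unit of randomisation is the clinic.
- **Analysis set (final paragraph).** The analysis is described as intention-to-treat, and the set is then defined: "All patients who consented and met the inclusion criteria will be included in the analysis per the group they were recruited into".
- **Covariates (end of the modelling paragraph).** "Demographic variables that are significantly different between groups (p < 0.05) will be included in a multivariable (adjusted) model". The baseline variables named as examples are sex, age, race, ethnicity and insurance. No migraine score is named, and the GLM for the primary and secondary outcomes has no stated baseline-outcome term.
- **Pre-post contrast (modelling paragraph).** "We will estimate average treatment effects (ATEs) to mitigate biases in intervention-control group comparisons", with this explanation: "These biases arise from permanent differences between the groups as well as biases in pre-post comparisons resulting from secular trends unrelated to the intervention". The estimator given for the simplest case is (Y12-Y11)-(Y22-Y21), written for practices. A semi-parametric causal analysis of practice-level outcomes is mentioned as conditional.

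The SAP does not say whether consent comes before or after site allocation, or whether recruiters and patients know the allocation.

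**The concern.** Randomising clinics makes clinics comparable in expectation. It does not by itself make the patients who consent within them comparable. If a clinic's arm is settled before its patients are approached, then who is identified, who is asked and who agrees can differ between arms. Intention-to-treat analysis deals with what happens after entry, such as exclusions and crossover. It says nothing about who enters.

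The analysis would then have to carry the protection. The covariate rule is poorly built for that. It covers demographics only, so a migraine severity score is outside it by definition. It also chooses by significance test, so an important imbalance can be missed when the test has little power. The pre-post contrast helps, but only against some kinds of imbalance. What is at stake is an apparent benefit or harm that reflects recruitment rather than the intervention.

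**Working it through.** The SAP gives no sample size, number of clinics, SD, correlation or effect size, so there is no figure of its own to reproduce. The check compares the bias of three analyses when the true effect is zero.

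**Inputs, all assumed.** Outcomes are in SD units, higher is worse, and the same patients are measured before and after. Pre-post correlation r = 0.6. One arm recruits patients whose baseline is worse by g = 0.1, 0.2, 0.3 or 0.5 SD. Demographics are unrelated to severity.

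**Analyses.** (a) Follow-up score adjusted for demographics only. (b) The SAP's contrast, the difference between arms in mean change. (c) Follow-up score adjusted for the baseline score.

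**Case 1: stable additive imbalance.** The arm is worse by g at both times.
- (a) g
- (b) g - g = 0
- (c) g - r·g = (1-r)g = 0.4g

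**Case 2: selection on the observed baseline (for example, patients recruited during a flare).** Baseline is shifted by g, but the expected follow-up is shifted only by r·g.
- (a) r·g = 0.6g
- (b) r·g - g = -(1-r)g = -0.4g
- (c) r·g - r·g = 0

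**Case 3: stable imbalance, with sicker patients improving more.** Assume a change of -0.3 per unit of severity. Follow-up is shifted by 0.7g, and the within-arm slope of follow-up on baseline is 0.7 × 0.6 = 0.42.
- (a) 0.7g
- (b) 0.7g - g = -0.3g
- (c) 0.7g - 0.42g = 0.28g

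| Bias in SD for g = 0.1 / 0.2 / 0.3 / 0.5 | (a) demographics only | (b) pre-post contrast | (c) baseline-adjusted |
|---|---|---|---|
| Case 1, stable | 0.10 / 0.20 / 0.30 / 0.50 | 0 / 0 / 0 / 0 | 0.04 / 0.08 / 0.12 / 0.20 |
| Case 2, observed baseline | 0.06 / 0.12 / 0.18 / 0.30 | -0.04 / -0.08 / -0.12 / -0.20 | 0 / 0 / 0 / 0 |
| Case 3, severity-dependent change | 0.07 / 0.14 / 0.21 / 0.35 | -0.03 / -0.06 / -0.09 / -0.15 | 0.03 / 0.06 / 0.08 / 0.14 |

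A simulation with 400,000 patients per arm agrees with every entry to within 0.01 SD. Clustering was not simulated; it would alter precision, not these biases.

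**Sensitivity to r in case 2.** With g = 0.5, the contrast's bias runs from -(1-0.4) × 0.5 = -0.30 at r = 0.4 to -(1-0.7) × 0.5 = -0.15 at r = 0.7.

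Two things follow. Demographic adjustment alone has the largest bias in every case. Between (b) and (c), neither is unbiased throughout: (b) is right in case 1, (c) is right in case 2, and in case 3 they err by similar amounts in opposite directions.

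**The case against.** The strongest reply is that the SAP expects differences between the groups and names an estimator against them. That stands. A reader might infer that demographic adjustment is the only correction, so that any severity imbalance goes straight into the result. The modelling paragraph does not support this: the contrast (Y12-Y11)-(Y22-Y21) is aimed at permanent group differences and removes a stable additive one. Nor does the SAP claim that its intention-to-treat set is free of selection bias.

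A reader might also infer that a group recruited with worse scores must regress further toward the mean. That holds only if selection acts on the observed or transient score. A stably sicker group regresses toward its own mean, and no differential shift follows.

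Thirdly, consent after allocation is inferred from the phrase about the group patients were recruited into. It is the natural reading, but not a stated fact. Recruitment procedure and concealment belong to the protocol, so their absence here is no fault of the SAP.

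Finally, adjusting for baseline can do worse than the SAP's contrast when the imbalance is stable (0.04 to 0.20 SD against 0). That is a good reason not to swap one for the other.

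What survives is narrower. The covariate rule is SAP content and is badly fixed. The contrast is written for practices and only for the simplest case, is not tied to the GLM, and does not cover cases 2 and 3. The causal analysis is conditional and limited to practice-level outcomes.

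**Conclusion.** The point holds as a partial gap in protection. The set is defined by consent under site randomisation, so if consent follows allocation, the intention-to-treat label does not guarantee comparable patients. The covariate rule shuts out the baseline outcome by design, and the pre-post contrast covers stable additive differences only. Under selection on the observed baseline, the contrast is biased by -(1-r)g, or -0.04 to -0.20 SD for g of 0.1 to 0.5 SD at r = 0.6. If the worse patients are in the intervention arm this looks like benefit; if they are in the control arm it looks like harm or hides a benefit.

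The values of g, r and the severity slope are assumptions, and nothing in the SAP shows that differential recruitment will occur. The fault in the covariate rule does not depend on those values. The rule should be changed before the analysis.

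**What to change.** 1. **Replace the p < 0.05 rule** at the end of the modelling paragraph with a pre-specified covariate set, included whatever the p-values: the baseline value of the outcome where it is measured; the site randomisation factors (location, volume and patients per provider) as far as the number of sites allows; and a short fixed list such as age, sex and insurance.
2. **Keep the pre-post contrast as a stated companion analysis.** Say how it relates to the GLM, report both results, and treat disagreement between them as a sign of baseline imbalance.
3. **Clarify the analysis set** in the final paragraph: patients are analysed by the arm to which their clinic was randomised. Show baseline scores by arm.

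Item 1 carries the point; item 3 is clarification and reporting. No extra patients and no change to consent are needed. The cost is a few more model terms, which may be tight if there are few sites. Baseline adjustment leaves some bias when a stable severity imbalance exists, which is why both analyses should be reported. Neither removes selection on unmeasured factors.

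### Carrying the last questionnaire forward sets later change to zero and can bias the between-arm comparison of survey outcomes

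*SAP*

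**What the plan says.** The SAP's paragraph on intention-to-treat and missing data notes that "inclusion of only patients who completed all 3 sets of questionnaires could bias results toward improvement". It continues: "To minimize this potential bias, a last observation carried forward (LOCF) technique will be applied". The one check visible is this: "Results from the LOCF technique will be further compared to those from the measured data". The text then breaks off mid-word, so anything that followed is unknown. The sentence adopting LOCF is complete.

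The preceding paragraph describes the effect as a difference in differences: "program effects are assessed by comparing pre-post differences in outcomes between practices exposed" and those not exposed. It gives this form as the simplest case. It chooses the form partly to guard against "biases in pre-post comparisons resulting from secular trends unrelated to the intervention".

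The visible text gives no reason to expect scores to stay fixed after a patient's last questionnaire. It names no likelihood-based, multiple-imputation or missing-not-at-random analysis.

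**The concern.** LOCF fills each missing later score with the last one recorded, so it sets all later change to zero. If the effect is a difference in change, that is a substantive assumption about the outcome itself. The SAP allows for time trends that affect both groups, so zero movement in dropouts is not an obvious default.

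Two consequences follow. With equal dropout and a real effect that dropouts share, LOCF dilutes the effect. If dropout rate, timing or trajectory differs between arms, LOCF can shift the difference in either direction, even with no effect at all. Clinics rather than patients are allocated here, and nothing in that design guarantees similar questionnaire return in the two arms.

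The planned comparison with the measured data can show that the choice of method matters. It cannot show which answer is right, because neither analysis holds any information on what dropouts did after their last questionnaire.

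**Working it through.** The SAP states no dropout rate, SD, sample size or scale, so there is no figure of its own to reproduce. From the SAP come the three questionnaires, the LOCF rule and the difference-in-change contrast. Every number below is an assumption chosen for illustration. Lower scores are better, and the intervention arm is listed first.

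**Formula.** Let ch be the true mean change from first to last questionnaire in an arm. Let d be the share missing the last questionnaire and u their mean change after their last completed one. Then

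LOCF difference = (chT - chC) - (dT × uT - dC × uC).

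Suppose dropouts follow the arm's mean course, half leave after baseline, half leave after the second questionnaire, and half of the change has occurred by then. Then u = ch × (0.5 + 0.5 × 0.5) = 0.75 × ch.

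**No true effect, both arms change by -3 (u = -2.25).**
- 20% vs 25%: -(0.20 × -2.25 - 0.25 × -2.25) = -0.1125.
- 15% vs 35%: -(-0.3375 + 0.7875) = -0.45; reversed, +0.45.
- 25% in both arms, all intervention dropouts leaving late (u = -1.5) and all control dropouts early (u = -3): -(-0.375 + 0.75) = -0.375.

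**True difference -2 (changes -5 and -3, so u = -3.75 and -2.25).**
- Equal dropout d gives -2 × (1 - 0.75d): -1.85 at 10%, -1.625 at 25%, -1.40 at 40%.
- 30% vs 15%: -2 - (-1.125 + 0.3375) = -1.2125.
- 15% vs 30%: -2 - (-0.5625 + 0.675) = -2.1125.

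**Simulation.** The closed form treats dropout as unrelated to outcome. The simulation makes dropout likelier after a worse last score (log-odds up by 1 per SD). It uses 6,000 runs, 150 independent patients per arm, normal scores with SD 5, and correlation 0.6 between questionnaires.

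| Dropout | True difference | LOCF, closed form | LOCF, simulated |
|---|---|---|---|
| 25% / 25% | 0 | 0.00 | 0.00 |
| 20% / 25% | 0 | -0.11 | -0.19 |
| 15% / 35% | 0 | -0.45 | -0.69 |
| 35% / 15% | 0 | +0.45 | +0.69 |
| 25% / 25%, late vs early | 0 | -0.375 | -0.35 |
| 25% / 25% | -2 | -1.625 | -1.62 |
| 30% / 15% | -2 | -1.21 | -1.02 |
| 15% / 30% | -2 | -2.11 | -2.30 |

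Monte Carlo error is about 0.007 for LOCF. In the last three rows the completers-only estimates were -1.99, -1.88 and -2.12, each nearer the truth than LOCF. A likelihood estimate was within 0.02 of the truth throughout. At 25% / 25% with a true -2, LOCF's average standard error was 0.514 against a sampling SD of 0.517, so the fault is bias and not the standard error. The simulation has no site clustering, so its standard errors do not carry over to this trial.

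**The planned check.** Let all dropout follow baseline, at 35% vs 15%, with completers changing by -5 and -3. LOCF gives 0.65 × -5 - 0.85 × -3 = -0.70, and completers give -2.00, whatever the dropouts did. The truth depends on the dropouts:
- they change like completers: -2.00;
- half as much: (-3.25 - 0.875) - (-2.55 - 0.225) = -1.35;
- not at all: -0.70;
- they worsen by 2: (-3.25 + 0.70) - (-2.55 + 0.30) = -0.30.

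The two planned results are the same in all four situations. In the last one the truth lies outside the range between them.

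**The case against.** The strongest defence is the plan's own rationale. It suspects that completers look better than dropouts would have, and on that belief LOCF can do well. In the last calculation above it is exact if dropouts do not change, nearer than completers if they worsen, and equally far off (0.65 each) if they change half as much. This stands, and it is why no-change belongs in the sensitivity analysis. But doubting completers does not establish exactly zero change in both arms.

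Second, the difference-in-differences sentence concerns practices, in the simplest case, and does not say that questionnaire scores carry a secular trend. That is fair as a reading of the text. The algebra does not depend on it, because the same bias enters any comparison of the arms at the last questionnaire.

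Third, the simulation makes dropout depend only on observed scores, so the likelihood method succeeds by construction. This is true. That method cannot see what dropouts did either, and its assumption can also fail.

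Fourth, the size is unknown and may be small. At 20% against 25% the bias of 0.11 to 0.19 is 0.02 to 0.04 of an SD of 5. With balanced dropout and trajectories LOCF creates no false effect and only dilutes a real one. All of this stands and limits the weight of the point.

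Finally, the lost text may contain further sensitivity analyses. That could reduce what needs adding, but it does not undo the adoption of LOCF.

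**Conclusion.** The concern holds for survey outcomes. LOCF is the stated remedy, and it biases the between-arm difference unless dropouts stay unchanged after their last questionnaire, dropout rate, timing and trajectories match across arms, or dT × uT happens to equal dC × uC, which no plan can count on. Neither its direction nor its size in this trial can be computed from the SAP. On the assumed values, equal dropout of 10% to 40% removes 7.5% to 30% of a real effect (0.75 × d), and a 20-point dropout gap with a common change of -3 shifts the difference by 0.45 to 0.69. The SAP does not say whether a survey outcome is primary. The plan should be changed, but nothing here shows that the trial's main conclusion is at risk.

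**What to change.** For survey outcomes, make the main analysis a likelihood-based repeated-measures model on all available questionnaires, with arm, time and arm-by-time terms, a suitable link and distribution, and allowance for site clustering. Multiple imputation that respects the clustering is an acceptable alternative. Add a delta-adjusted missing-not-at-random sensitivity analysis in which the shift varies separately by arm and the no-change case is included. Report the share missing each questionnaire by arm. Keep LOCF only as a secondary sensitivity analysis. State which records the measured-data comparison covers, unless the lost text already does.

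The cost is SAP wording and modest extra programming, with no new data. In exchange the main analysis rests on a missing-at-random assumption, which may also be wrong and which the delta-adjusted analysis is there to probe.

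### For survey outcomes, agreement between the LOCF and measured-data results cannot show that loss to follow-up was harmless; a delta-adjusted analysis is needed beside it

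*SAP*

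**What the plan says.** The relevant text is the SAP's unnumbered paragraph on intention-to-treat and missing data. It sets the analysis population: "All patients who consented and met the inclusion criteria will be included in the analysis per the group they were recruited into". It then warns, for survey data, that "inclusion of only patients who completed all 3 sets of questionnaires could bias results toward improvement". The remedy follows: "To minimize this potential bias, a last observation carried forward (LOCF) technique will be applied". The last visible sentence gives the check on that remedy: "Results from the LOCF technique will be further compared to those from the measured data to assess the impact of loss to follow". The text stops mid-word at that point.

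The sentence gives the comparison a purpose, namely to judge what loss did to the results. It does not say how close the two results must be, or what will be concluded if they are close or far apart. The visible text contains no analysis under another assumption about lost patients' outcomes, and no comparison of loss between arms.

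**The concern.** The impact of loss depends on the scores that lost patients would have given later. The measured-data result takes the lost patients to resemble those who stayed. LOCF takes them not to have changed since their last questionnaire. Neither uses any information on their later scores, so comparing the two cannot reveal whether those scores would have changed the answer.

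The SAP's own warning makes this matter more. It expects that restricting to patients with all 3 questionnaires may overstate improvement, so it expects loss to be related to outcome. If some patients improve by the second questionnaire, worsen and are then lost, LOCF carries the improvement forward and reproduces the bias it was meant to reduce. The two results can then agree and both be wrong. What is at stake is the robustness statement for survey outcomes, which would rest on a comparison that cannot support it.

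**Working it through.** **Inputs.** From the SAP: 3 questionnaire sets, LOCF, the comparison with measured data, and an effect measured as a difference in differences ("program effects are assessed by comparing pre-post differences in outcomes between practices exposed" and not exposed). The SAP gives no dropout rate, scale or effect size, so there is no planned figure to reproduce. Assumed here: loss of 10% to 40%, and mean changes of -2 and -3 on an arbitrary scale where negative means improvement. The measured-data result is taken as the mean change among patients with a final questionnaire.

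**Formulas, within one arm.** Let *d* be the proportion lost, *c* the mean final change of completers, *l* the mean last recorded change of lost patients, and *u* their unseen mean final change.

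- Measured = *c*
- LOCF = (1 - *d*)*c* + *d l*
- Truth = (1 - *d*)*c* + *d u*
- LOCF - measured = *d*(*l* - *c*)
- Bias of measured = *d*(*c* - *u*); bias of LOCF = *d*(*l* - *u*)

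The gap between the two results does not contain *u*. Both biases do. The effect is the intervention value minus the control value.

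**Agreement with a biased result.** Intervention: *c* = *l* = -3, and lost patients return to baseline (*u* = 0). Control: *c* = *l* = *u* = -2. At *d* = 0.30:

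- Measured = -3 - (-2) = -1.0
- LOCF = (0.7 × -3 + 0.3 × -3) - (-2) = -1.0
- Truth = (0.7 × -3 + 0.3 × 0) - (-2) = -0.1

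Of the apparent effect, 0.9 out of 1.0 comes from loss, and the gap is zero. In general the truth here is -1 + 3*d*:

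| Loss per arm | Measured | LOCF | Truth |
|---|---|---|---|
| 10% | -1.0 | -1.0 | -0.7 |
| 20% | -1.0 | -1.0 | -0.4 |
| 30% | -1.0 | -1.0 | -0.1 |
| 40% | -1.0 | -1.0 | +0.2 |

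**The same gap from different truths, 30% loss per arm.**

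*Random loss straight after baseline, true effect -1.* Intervention *c* = *u* = -3, control *c* = *u* = -2, and *l* = 0 in both.

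- Measured = -3 - (-2) = -1.0
- LOCF = 0.7 × (-3) - 0.7 × (-2) = -0.7
- Truth = -1.0

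*True effect 0.* In both arms everyone has changed by -3 at the second questionnaire, and 30% then relapse to +0.33, so the true mean change is 0.7 × (-3) + 0.3 × 0.33 = -2.0. The intervention arm loses exactly the relapsers (*c* = *l* = -3). The control arm loses 30% at random (*c* = *u* = -2, *l* = -3).

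- Measured = -3 - (-2) = -1.0
- LOCF = -3 - (0.7 × -2 + 0.3 × -3) = -3 - (-2.3) = -0.7
- Truth = -2 - (-2) = 0

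Both trials show the pair -1.0 and -0.7. In the first, measured data are right and LOCF is biased. In the second, both are biased. The comparison cannot tell them apart.

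**The case against.** The strongest reply is that the SAP promises only to compare two results. Setting them side by side satisfies the sentence, and two methods with different assumptions are a limited but real sensitivity check. That stands as far as it goes, and the comparison is worth keeping as description. It does not meet the point, because the sentence gives the comparison the job of assessing the impact of loss.

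Several stronger readings are tempting and are not supported:

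- *That this is the only planned check.* The available text breaks off inside this sentence and the protocol is not at hand. One can say only that no other check is visible.
- *That the plan would report little impact whenever the results are close.* It contains no such rule and no criterion for closeness.
- *That the check raises false alarms when loss did no harm.* Under random loss after baseline, LOCF moves from -1.0 to -0.7. LOCF is the method the plan applies, so loss did distort that result and the gap exposes it. What fails is the attribution: the gap does not say which result is wrong.
- *That improvement followed by relapse is the usual course in an unblinded programme.* The SAP describes neither blinding nor a pattern of dropout. The illustration shows what is possible, not what is likely.

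It is also fair to say that a tipping-point analysis holds no information on lost patients' scores either. Its advantage is that it varies the assumption over a stated range and shows where the conclusion changes, whereas the planned comparison looks at two fixed assumptions.

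**Conclusion.** The point holds for survey-collected outcomes. Close agreement between LOCF and measured-data results does not show that loss was harmless, and a gap does not show which result is biased. This follows from the algebra and does not depend on the assumed numbers.

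The size does depend on them. With last recorded changes of -3 and -2 and every lost intervention patient returning to baseline while lost control patients hold their change, the two results agree at -1.0 while the truth runs from -0.7 at 10% loss to +0.2 at 40%. Milder relapse, or relapse in both arms, would give a smaller distortion.

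A reader might infer that the main survey estimate is wrong, or that the primary outcome is affected. Neither follows: the SAP does not name the primary outcome, and nothing here shows how much loss occurred. The defect is in the robustness check, and it is worth correcting because the correction is cheap.

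**What to change.** 1. Keep the LOCF versus measured-data comparison, label it descriptive, and state that agreement will not be read as absence of impact.
2. Report the proportion lost by arm and by questionnaire set.
3. Add a prespecified delta-adjusted (tipping-point) analysis for the survey outcomes. Impute missing questionnaires from observed scores with a model that respects clinic clustering. Shift the imputed intervention-arm values stepwise toward worse, up to return to baseline, and report the shift at which the conclusion changes.

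In the 30% illustration, imputed changes start at -3 and -2, and a shift of δ in the intervention arm gives an effect of -1 + 0.3δ. Shifts of 0, 1, 2 and 3 give -1.0, -0.7, -0.4 and -0.1, the last being return to baseline. A reader can then judge whether the shift that changes the conclusion is credible.

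The cost is a change of SAP wording and some extra analysis, with no new data collection. The downside is that a range of estimates may look less favourable than a single statement that two results agree.
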